5.1 Additional Study Sites

No additional study sites.

6. Study Population

60 males with ED of organic origin. All patients will be regular PDE5i users/responders. Men with ED will be evaluated by IIEF-EF domain and eligible patients will be randomized to one of 2 treatment groups with an equal allocation ratio (1:1). Participants who do not meet eligibility criteria will be considered a screen failure and will not receive the study therapy.

6.1 Inclusion criteria:

In order to participate in this study, a patient must:

- 1) Be Male
- 2) Be 30 to 80 years of age (inclusive).
- 3) Be able to provide written informed consent.
- 4) Have a diagnosis of mild to moderate ED (12-21) or mild ED (22-25) based on IIEF-EF questionnaire score.
- 5) Be in a stable heterosexual relationship, and have a minimum of 2 sexual attempts per month for at least one month prior to enrollment..
- 6) Agree to comply with all study related tests/procedures.

6.2 Exclusion criteria:

In order to participate in this study, a patient must not have any of the following:

- 1) Previous penile surgery of any kind (except circumcision and condyloma removal), such as penile lengthening, penile cancer surgery, penile plication, grafting.
- 2) Previous history of priapism, penile fracture, Peyronie's Disease, or penile curvature that negatively influences sexual activity,
- 3) Abnormal morning serum testosterone level defined as a value lower than 300 ng/dL ($\pm 5\%$).
- 4) Psychogenic ED as determined by study investigator.
- 5) Patients using ICI for management of ED
- 6) Patients with generalized polyneuropathy, neurological conditions, or psychiatric disease (such as bipolar disorder or depression).

- 7) Have a serious comorbid illness or condition that, in the opinion of the investigator, may compromise the safety or compliance of the subject or preclude successful completion of the study.
- 8) History of consistent treatment failure with PDE5 inhibitors for therapy of ED.
- 9) Poorly controlled diabetes as indicated by Hemoglobin a1c > 9%.
- 10) Use of antiplatelet medication

7. Identification and Enrollment of Subjects

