ROUTE OF ADMINISTRATION	Intracavernosal Injection (PRP) + extracorporeal shockwave therapy (SWT)
SUBJECT POPULATION	60 male subjects between the age of 30-75 with Mild or Mild-to-Moderate ED
STUDY OBJECTIVES	
Primary: To investigate and compare the treatment efficacy of PRP injection + SWT vs placebo injection / SHAM treatment in men with mild-moderate ED, as measured by IIEF.
 
Secondary: To study incidence of adverse events and safety of PRP injection + SWT treatment in men with mild-moderate ED, as measured by IIEF.

INVESTIGATION PLAN	
60 men with Erectile Dysfunction (ED) of organic origin, that meet all of the inclusion and none of the exclusion criteria, will be randomized to receive either PRP+SWT, or placebo/sham in a 1:1 double-blinded fashion.
 
a) Group A (30 subjects): Autologous PRP injection + SWT therapy. All subjects in this group will receive 2 sessions of autologous PRP penile injection with 30 ± 7 day treatment interval. 5mL of PRP will be injected at each session. Additionally, patients will receive a total of 3600 shocks over a five-week period, starting at initial PRP injection.
 
b) Group B (30 subjects): Placebo (Normal Saline) + SHAM. All subjects in this group will receive 2 sessions of normal saline penile injection with 30 ± 7 day treatment interval. 5mL of normal saline will be injected at each session. Additionally, patients will receive SHAM treatment over a five-week period, starting at initial placebo injection.

DURATION OF STUDY	7 months (1 month screening, 5 weeks of therapy sessions, 6 months of follow-up).

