2.4 Combination Restorative Therapy for Erectile Dysfunction

The development of ED therapeutics that focus on neurovascular regeneration and repair strategies are of great importance. A large body of *pre-clinical* work has demonstrated the effect of SWT alone (monotherapy) on angiogenesis and progenitor / stem cell recruitment for ED [2, 3, 8-11]. PRP monotherapy importantly is also supported by well-defined mechanistic insights obtained from rigorously conducted animal studies [12-19]. All the previous studies in humans have evaluated either IIEF scores and / or penile Doppler ultrasound hemodynamic parameters, but there has not been evaluation of the treatment as a combination. The proposed mechanisms of both interventions would

suggest that the combination therapy would act in a synergistic manner, with superiority over monotherapy. Success of our proposed work could fundamentally change the standard of care for ED and substantially improve the quality of life for tens of millions of men.

3. Study Objectives

3.1 Primary Objective:

To investigate and compare the safety of PRP and SWT vs placebo/sham treatment in men with mild-moderate ED.

3.2 Secondary Objective:

To study the treatment efficacy of PRP and SWT treatment vs placebo/sham treatment in men with mild-moderate ED.

4. Study Endpoints

4.1 Primary Endpoint (safety):

- Incidence of treatment emergent serious adverse events (TE-SAEs) in all patients during the study period. Adverse events will be recorded at every visit. The following contains a list of the anticipated adverse events:
 - Pain
 - Bruising
 - Swelling
 - Edema
 - Allergy
 - Penile Fracture
 - New Penile Curvature

4.2 Secondary Endpoints (efficacy):

- Change in IIEF-EF score from baseline to 3 and 6 months post-therapy compared to control group.
- Percentage of subjects that achieve minimal clinically important difference (MCID) in IIEF-EF from baseline to 3 and 6 months post-therapy compared to control group,
- Percentage of subjects who either decrease or discontinue use of PDE5i after three months post-therapy compared to control group.

4.3 Exploratory Endpoints:

- Differences in Doppler ultrasound parameters (PSV and EDV) from baseline to 6 months post-therapy compared to control group.
- Treatment satisfaction as assessed by EDITS questionnaire in all subjects.
- Changes in IPSS questionnaire between treatment and control group.
- Perceptions of therapeutic allocation between treatment and control group.

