7.1 Recruitment and Pre-screening

The research coordination team may develop materials to aide in recruitment. This may include, but is not limited to, informational videos and brochures which provide education about erectile dysfunction and include information about the study; physician referral letter templates which can be used to promote awareness of the study in the urology community; flyers/posters which can be utilized at approved clinic locations and as part of health fair materials; templates for print advertisements which can be utilized in newsprint and media campaigns. Not all materials have been developed prior to trial initiation, however each of these recruitment methods will be reviewed and approved by the IRB prior to use.

Pre-screening of subjects includes reviewing medical records and imaging studies for inclusion/exclusions prior to consent. From the review of subjects' medical records and imaging studies on file, subjects who are determined to have a diagnosis of erectile dysfunction of organic origin, and have mild-moderate erectile function as assessed by IIEF-EF, as stated in Section 6.1, and also do not have evidence in their medical record of study exclusions stated in Section 6.2, are eligible to be consented to the study.

Investigators will inform research staff of potential participants who have been identified through pre-screening so the subjects can be approached to discuss the study and conduct the informed consent session. No study procedures will take place prior to the subjects signing of the informed consent form.

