7.4 Withdrawal Criteria

All subjects who either screen fails, is withdrawn from the study, or has completed all visits should be de-enrolled from the research database within 2 business days, in accordance with university policies (or respective institutional policy).

Subjects may be withdrawn from the study for any of the following reasons:

- a) A subject does not meet the eligibility criteria (the subject will be considered a screen failure).
- b) A subject withdraws consent.
- c) If a new treatment for erectile dysfunction is made available during the study duration, the investigator will inform the patient at a follow-up visit, and be offered withdrawal to utilize new treatment.
- d) A subject expires during protocol participation from causes other than the study treatment (not due to adverse events).
- e) At the discretion of the principal investigator for issues of non-compliance, or other behavioral factors.

8. Procedures Involved

60 men with Erectile Dysfunction (ED) of organic origin, that meet all of the inclusion and none of the exclusion criteria, will be randomized to receive either PRP+SWT, or placebo/sham in a 1:1 double-blinded fashion.

- a) Group A (30 subjects): Autologous PRP injection + SWT therapy. All subjects in this group will receive 2 sessions of autologous PRP penile injection with 30 ± 7 day treatment interval. 5mL of PRP will be injected at each session. Additionally, patients will receive a total of 3600 shocks over a five-week period, starting at initial PRP injection.
- b) Group B (30 subjects): Placebo (Normal Saline) + SHAM. All subjects in this group will receive 2 sessions of normal saline penile injection with 30 ± 7 day treatment interval. 5mL of normal saline will be injected at each session. Additionally, patients will receive SHAM treatment over a five-week period, starting at initial placebo injection.

8.1 Schedule of Events:

The events table for the conduct of this study is shown below:

Table 1:

Schedule of Events		Screening	Treatment					Follow Up	
Time Point		0-30 days before randomization	Week 1	Week 2	Week 3	Week 4	Week 5	Month 3	Month 6
Event			Day 0	Day 7 \pm 2	Day 14 \pm 2	Day 21 \pm 2	Day 28 \pm 2	Day 90 \pm 14	Day 180 \pm 14
Informed Consent		X							
Demographics		X							
Medical History		X							
Physical Exam		X							
Doppler Ultrasound		X							X
Questionnaires	IIEF	X						X	X
	EDITS							X	X
	VAS		X	X	X	X	X		
	IPSS	X							X
	SGA								X
Laboratory Tests		X							

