- 8.2.13 *PRP/Placebo Injection:*** Approximately 120mL of blood will be collected from participants for preparation of investigational product. Refer to Section 9.2 for description of IP preparation and administration.

8.2.14 Concomitant Medications: Review of current use of prescription and over the counter (OTC) medications. Participants must discontinue use of PDE5i medications throughout the duration of the study.

8.2.15 Review Adverse Events: Refer to Section 12 for description and reporting of adverse and serious adverse events.

8.2.16 SWT/Sham Treatment: In the treatment group, patients randomized will receive 5 weekly sessions, in which 720 shocks of treatment energy will be applied in every session to each treated region (left and right corpora cavernosa and crura). In the sham group, patients will have the same number of sessions, and the machine will be set to deliver 720 shock treatments, but the machine will not fire shockwaves.

8.2.17 Laboratory Testing: Hematology, chemistry, hemoglobin A1C, and serum testosterone lab test results will be collected at screening. If any standard of care labs testing have been performed within 12 months of the date of the screening visit, those results may be used for the purpose of this study.

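### The eligibility criteria do not enforce the Section 6 statement that all men are regular PDE5i users and responders, which leaves the PDE5i-reduction endpoint without a defined denominator

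*Combined protocol and SAP*

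**What the plan says.** **PDE5i status.** Section 6 (Study Population) describes the 60 men in one sentence: "All patients will be regular PDE5i users/responders". The six inclusion criteria, in the synopsis and in Section 6.1, do not mention PDE5i. The only criterion that does is exclusion 8: "History of consistent treatment failure with PDE5 inhibitors for therapy of ED".

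**What admits a man.** Section 7.1 makes a man eligible for consent if he has organic ED, meets the severity requirement ("have mild-moderate erectile function as assessed by IIEF-EF, as stated in Section 6.1") and has no Section 6.2 exclusion on record. Section 8 says that men "that meet all of the inclusion and none of the exclusion criteria, will be randomized to receive either PRP+SWT, or placebo/sham". Section 6 defines a screen failure as not meeting the eligibility criteria.

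**Where PDE5i use matters later.** A secondary endpoint in Section 4.2 and the synopsis is: "Percentage of subjects who either decrease or discontinue use of PDE5i after three months post-therapy compared to control group". Section 8.2.14 says: "Participants must discontinue use of PDE5i medications throughout the duration of the study".

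**Age.** The synopsis population is "60 male subjects between the age of 30-75 with Mild or Mild-to-Moderate ED". Inclusion criterion 2, in the synopsis and in Section 6.1, reads "Be 30 to 80 years of age (inclusive").

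**The concern.** The population sentence and the criteria describe different sets of men. Only the criteria are used to decide who is consented and randomised, so the sentence has no step that puts it into effect.

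This matters because one secondary endpoint presupposes baseline PDE5i use. A man who takes no PDE5i has nothing to decrease or discontinue. If such men enter, the percentage could be taken over all randomised men or over baseline users only. The plan does not choose, and Section 14.1 names tests without defining the analysis set for this endpoint.

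Separately, if every participant stops PDE5i for the duration of the study, the endpoint records compliance with an instruction and cannot show a treatment effect.

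The age mismatch leaves men aged 76 to 80 inside one description and outside the other.

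**Working it through.** **1. Can a non-user pass?** Take a man of 60 with organic ED, an IIEF-EF score of 20 and a stable heterosexual relationship with the required attempts, who has never taken a PDE5i.

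- Inclusion 1 to 6: met, since none concerns PDE5i.
- Exclusion 8: not triggered, since a man with no treatment history has no history of failure.
- Other exclusions: none concerns PDE5i.
- Sections 7.1 and 8: no further PDE5i check.

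He can be randomised, contrary to Section 6. The same holds for an occasional user who has not consistently failed. Exclusion 8 goes part of the way towards 'responders' but does nothing for 'regular users'.

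**2. Sample size inputs.** Section 14.2 reproduces from its own formula: 2 × (1.96 + 0.84)² × 0.25 × 0.75 / 0.35² = 24.0 per group, and 24 / (1 − 0.20) = 30 per group. PDE5i use does not enter this formula, so the point does not change the planned 60.

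**3. Effect on the PDE5i endpoint.** Let f be the share of non-users, equal in both arms. The documents give no value, so f is an assumption. Men per arm who can meet the endpoint = n × (1 − f):

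| f | of 30 randomised | of 24 completers | highest possible percentage over all men |
|---|---|---|---|
| 0% | 30 | 24 | 100% |
| 10% | 27 | 21.6 | 90% |
| 20% | 24 | 19.2 | 80% |
| 30% | 21 | 16.8 | 70% |
| 50% | 15 | 12 | 50% |

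Over all men, a between-arm difference D among users appears as (1 − f) × D. Over users only, D is preserved but rests on the smaller counts.

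**4. The discontinuation rule against the endpoint.** The schedule follows men to Month 6, so the three-month assessment falls within the study. If Section 8.2.14 is followed literally, every baseline user in both arms has discontinued by then. The percentage among users is 100% in each arm and the difference is zero by construction.

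**5. Chance imbalance in user status.** Section 9.3 describes 1:1 randomisation and no stratification. With 60 men, 30 per arm and K non-users in total, the number X in one arm is hypergeometric. The arms differ by 6 or more men (20 percentage points) when |2X − K| ≥ 6:

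| Non-user share (assumption) | K | Probability |
|---|---|---|
| 10% | 6 | 0.024 |
| 20% | 12 | 0.104 |
| 30% | 18 | 0.158 |
| 50% | 30 | 0.196 |

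This is random imbalance, not bias. The documents give no figure for the effect of stopping a PDE5i on IIEF-EF, so no shift in score is computed.

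**6. Age.** Synopsis population: 30 to 75. Synopsis criterion 2 and Section 6.1: 30 to 80 inclusive. The conflict covers ages 76 to 80 and exists within the synopsis itself.

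**The case against.** The Section 6 sentence is protocol text placed directly above the criteria, so investigators may apply it in practice, and exclusion 8 already removes consistent failures. This stands in part. It means that the documents do not show that non-users will enrol. It does not close the gap, because Sections 7.1 and 8 point to the criteria alone.

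A reader might infer that the efficacy result will be claimed for PDE5i responders and that a mixed population would undermine it. The documents do not support this. Section 3.2 and the synopsis state the efficacy population as men with mild-moderate ED, with no reference to PDE5i response.

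A reader might also infer that mixing users and non-users biases the IIEF-EF comparison. Randomisation prevents systematic bias from this source, and chance imbalance is part of the ordinary uncertainty of the comparison. An on-drug baseline for users is possible: Section 8.2.7 allows an IIEF from the past 6 months, and no PDE5i-free period before baseline is stated. The documents do not say that baseline is scored on drug, so no size can be attached.

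Current medication is already reviewed at screening under Section 8.2.14 and the schedule of events. This stands and makes the fix cheaper, although response to PDE5i is not explicitly recorded.

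The age conflict is small, since both criteria lists agree and only the population line differs. This stands too.

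**Conclusion.** The point holds in this form: the criteria allow a population other than the one Section 6 states. It would go too far to say that the enrolled population is not the stated one, since that depends on who is recruited.

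The supported consequence is limited to a secondary endpoint. With no non-users, all 30 men per arm could meet the PDE5i-reduction endpoint; at an assumed 10% to 50% non-users, 27 to 15 could. Which denominator applies is undefined. Whatever that share is, the endpoint conflicts with Section 8.2.14.

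The primary safety endpoint and the sample size formula are unaffected. The probability of a 20-point imbalance in user status runs from about 2% at 10% non-users to about 20% at 50%, and it describes noise only. The age mismatch is a minor inconsistency. The sponsor should correct these points, but they do not threaten the trial's primary aim.

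**What to change.** 1. Reconcile Section 6 with Sections 6.1 and 6.2 and the synopsis. Either list regular PDE5i use and response as a criterion, with the sponsor's definition of both terms, or delete the Section 6 sentence. The choice is the sponsor's.
2. If non-users are admitted, restrict the PDE5i-reduction endpoint to men using a PDE5i at baseline, identified from the screening medication review. Report the IIEF-EF results with baseline PDE5i use as a factor.
3. Reconcile Section 8.2.14 with the PDE5i-reduction endpoint. Restricting the denominator does not resolve that conflict.
4. State one age range throughout.

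**Cost.** A few lines in an amendment. Adding the criterion shrinks the eligible pool by the non-user share, which the documents do not give and which may not be small. Restricting the endpoint gives it a smaller denominator, as tabulated above, and so less precision. A baseline factor uses one degree of freedom in a 60-man trial.

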DEFINITION OF ENDPOINTS	
Primary:
 
 - Incidence of treatment emergent serious adverse events (TE-SAEs) in all patients during the study period. 
Secondary:
 
 - Change in IIEF-EF score from baseline to 3 and 6 months post-therapy compared to control group. - Percentage of subjects that achieve minimal clinically important difference (MCID) in IIEF-EF from baseline to 3 and 6 months post-therapy compared to control group, - Percentage of subjects who either decrease or discontinue use of PDE5i after three months post-therapy compared to control group. 
Exploratory:
 
 - Differences in Doppler ultrasound parameters (PSV and EDV) from baseline to 6 months post-therapy compared to control group. - Treatment satisfaction as assessed by EDITS questionnaire in all subjects. -

Protocol Synopsis	
INCLUSION CRITERIA	
 1. Be Male 2. Be 30 to 80 years of age (inclusive). 3. Be able to provide written informed consent. 4. Have a diagnosis of mild to moderate ED (12-21) or mild ED (22-25) based on IIEF-EF questionnaire score. 5. Be in a stable heterosexual relationship, and have a minimum of 2 sexual attempts per month for at least one month prior to enrollment. 6. Agree to comply with all study related tests/procedures.
EXCLUSION CRITERIA	
 1. Previous penile surgery of any kind (except circumcision and condyloma removal), such as penile lengthening, penile cancer surgery, penile plication, grafting. 2. Previous history of priapism, penile fracture, Peyronie's Disease, or penile curvature that negatively influences sexual activity, 3. Abnormal morning serum testosterone level defined as a value lower than 300 ng/dL ($\pm 5\%$). 4. Psychogenic ED as determined by study investigator. 5. Patients using ICI for management of ED 6. Patients with generalized polyneuropathy, neurological conditions, or psychiatric disease (such as bipolar disorder or depression). 7. Have a serious comorbid illness or condition that, in the opinion of the investigator, may compromise the safety or compliance of the subject or preclude successful completion of the study. 8. History of consistent treatment failure with PDE5 inhibitors for therapy of ED. 9. Poorly controlled diabetes as indicated by Hemoglobin a1c > 9%. 10. Use of antiplatelet medication

1. Protocol Title

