Randomization			X						
PRP/Placebo			X				X		
Shockwave/Sham			X	X	X	X	X		
Concomitant Medications/Therapy		X	X	X	X	X	X	X	X
Review Adverse Events			X	X	X	X	X	X	X

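### Exclusion 10 names antiplatelet drugs only; a man on an anticoagulant can be kept from bilateral corporal injections only through the investigator's discretion under exclusion 7

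*Combined protocol and SAP*

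**What the plan says.** Section 6.2 closes its list of ten exclusions with "10) Use of antiplatelet medication". The synopsis repeats it as "Use of antiplatelet medication". No reason is given for the criterion.

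The only other exclusion that could reach a man on an anticoagulant in general is number 7: "Have a serious comorbid illness or condition that, in the opinion of the investigator, may compromise the safety or compliance of the subject". It names no drug class.

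Both arms are injected. For the active arm, section 8 says "All subjects in this group will receive 2 sessions of autologous PRP penile injection"; for the control arm, "All subjects in this group will receive 2 sessions of normal saline penile injection". Section 9.2.1 splits each injection between the right and left corpus cavernosum and has saline given in the same way as PRP. The same section specifies a penile tourniquet, 20 minutes of manual compression, and a compressive dressing that the patient removes after 4 hours. Section 15.1 lists penile hematoma among the anticipated adverse events.

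On medication, the schedule of events has a row headed "Concomitant Medications/Therapy" that is marked at every time point. Section 8.2.14 describes the review and sets one drug rule: "Participants must discontinue use of PDE5i medications throughout the duration of the study".

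**The concern.** An injection into both corpora is a procedure with a recognized bleeding risk, and the protocol itself anticipates hematoma. One would expect the main drug classes that impair hemostasis to be handled by a written eligibility rule. One class is covered and the other is not. A stable man on an anticoagulant, otherwise eligible, meets no named exclusion, and two investigators could reasonably decide differently about him.

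What is at stake is participant safety in an elective, investigational procedure. Men in the control arm bear the same needle-related risk with saline, so they have no expected therapeutic gain to set against it. Safety is also the trial's primary objective in section 3.1, which makes a written rule preferable to case-by-case judgment.

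**Working it through.** The plan states no figure on this point, so there is none to reproduce. The check is mainly a reading of the text, with a small calculation to size the consequence.

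**1. Is there a named rule anywhere?**
- Synopsis criteria and sections 6.1 and 6.2: 0 of 10 exclusions name anticoagulants, a bleeding disorder or a coagulation threshold.
- Section 7.1: a man whose record shows none of the listed exclusions may be approached; such men, who "do not have evidence in their medical record of study exclusions stated in Section 6.2, are eligible to be consented to the study", are screened against 6.2 as it stands. This includes exclusion 7, so 7.1 adds no rule and removes none.
- Section 7.4 (withdrawal): no mention of drugs that affect bleeding.
- Section 8.2.14: the only drug to be stopped is PDE5i.
- Sections 8.2.17 and 8.3.1 (screening tests): hematology, chemistry, hemoglobin A1C, testosterone and prolactin; no coagulation test.
- Section 9.1: the only anticoagulant in the documents, the citrate dextrose added to drawn blood, which is not a patient medication.

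**2. Is the information available to apply a rule?** The medication review is marked at Screening, Days 0, 7, 14, 21 and 28, Month 3 and Month 6, which is 8 of 8 time points. Section 9.3 randomizes on Day 0 those who remain eligible, so a check at screening and again on Day 0 can be made before allocation.

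**3. How many men might be concerned?** The documents give no prevalence. Let p be the share of otherwise eligible men who take an anticoagulant, assumed to lie between 1% and 5%.
- Expected number among 60 enrolled if exclusion 7 is never applied to them: 60 × p.
- Extra screen failures needed to enroll 60 once they are excluded: 60/(1 − p) − 60.

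| Assumed p | Men among 60 | Extra screen failures |
|---|---|---|
| 1% | 0.6 | 0.61 |
| 3% | 1.8 | 1.86 |
| 5% | 3.0 | 3.16 |

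The middle column is an upper bound for each p, because any use of exclusion 7 lowers it.

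**4. What do the existing safety data say?** Sections 12.1 and 15.1 report 1 bruise in 75 men: 1/75 = 1.33%, exact (Clopper-Pearson) 95% interval 0.03% to 7.21%. The team's own PRP data in section 12.1 show 0.00% penile bruising. Neither source says whether any of these men took anticoagulants, so neither gives a rate for them.

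**The case against.** The case for leaving the criterion alone has substance.

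- **Mitigation exists.** The tourniquet, the compression, the dressing and the instruction to report problems are direct bleeding controls. This stands and lowers the severity. They act during and after the injection, however. They do not determine who is injected, and the protocol does not adapt them for a man on an anticoagulant.
- **Investigator discretion exists.** Since 8.2.14 requires only PDE5i to be stopped, a reader might infer that nothing would happen if an anticoagulant were found. The documents do not support that. Section 8.2.14 is equally silent on antiplatelet drugs, which still exclude a man through 6.2. Exclusion 7 gives a route to exclude, and section 6 then makes the man a screen failure who gets no study therapy. Exclusion 6 may also remove some of these men, depending on why they are treated. What remains is that exclusion 7 concerns an illness or condition and turns on opinion.
- **The criterion may have another purpose.** A reader might infer that exclusion 10 is a bleeding rule that contradicts itself by omitting a class. The protocol gives no reason for it, and it may protect the platelet product. No inconsistency is therefore claimed. If it does protect the product, no named criterion addresses medication-related bleeding at all, so the gap exists on either reading.
- **Harm is not quantified.** This stands. The few data cited are reassuring, and how much anticoagulation raises the risk under this compression procedure cannot be established from the documents.

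**Conclusion.** The point holds as a cheap improvement of low severity. No named criterion covers anticoagulants, both arms receive bilateral corporal injections twice, and the protocol anticipates hematoma, so the only general safeguard at entry is discretionary.

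The size rests on an assumed prevalence: 0.6 to 3.0 men in 60 for 1% to 5%, and fewer if exclusion 7 is used. It would be too strong to say that such men will be enrolled or harmed. Investigators may well exclude them in practice, and no probability of harm can be derived from what is given. No endpoint, power figure or analysis is affected.

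**What to change.** Change exclusion 10, in section 6.2 and in the synopsis, to: *Use of antiplatelet or anticoagulant medication.* Apply it at screening and again on Day 0 before randomization, using the medication review already scheduled. Add a sentence stating that a man must not stop a needed anticoagulant in order to qualify.

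The cost is two added words in two places and one sentence, by amendment, with no new test, visit or form. The downside is a slightly narrower population and a few more screen failures, about 0.6 to 3.2 per 60 enrolled under the assumed prevalence. Because the exclusion acts before allocation, it creates no partly treated men and raises no question for the analysis in section 14.1.

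Whether to withhold the second injection from a man who starts such a drug after Day 0 is a separate, optional decision for the investigator. It would be a treatment-discontinuation rule rather than an eligibility criterion, and it is not part of this recommendation.
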